5.3. Baseline and Other Assessments

A complete medical history and demography (gender, age, race, and ethnicity) will be collected at the screening visit. Medications being taken by the subject in the 7-day period prior to the first vaccination through the completion of the study along with complete immunization history will be recorded and reported on an eCRF.

Vitals signs, full physical examinations and hematocrit and total protein determinations as part of the routine plasmapheresis will be assessed during pre-donation screening.

Infectious disease testing will be performed on all plasma samples collected from plasma donations and if a subject is positive for any of these infectious diseases, they will be taken off study. In addition, RPR (syphilis test) is performed every 4 months. If the subject is a first time donor, they must have two sequential plasma donations that are negative for the following infectious diseases to be eligible for plasmapheresis: Anti-HIV-1/2, HBsAg, Anti-HCV, SPE/RPR, Indirect Coombs, and PCR testing for HIV-1, HBV and HCV, HAV, and Parvovirus B19.

An eligibility checklist will be completed at screening. If the subject is not eligible for the study, a Reasons Not Eligible eCRF will be completed.

A dipstick urinalysis will be performed that tests for protein, blood, leukocyte esterase, nitrates, pH, specific gravity, ketones, bilirubin, and glucose. A blood sample will also be collected for a serum creatinine test. These tests will be performed to monitor for the possible development of immune complex-mediated glomerular disease.

Anti-diphtheria antibody levels will be measured at a central laboratory using the EUROIMMUN Anti-Diphtheria Toxoid ELISA (IgG). High anti-diphtheria titers will be assessed for an association with an increase in reactogenicity.

6. Hypotheses to be Tested

Hypothesis tests will be performed in order to determine if there is an association between reactogenicity and anti-diphtheria titers. Null Hypothesis of no association between reactogenicity and anti-diphtheria titers will be tested on Slope obtained using simple linear regression analysis at alpha=0.01 using two-sided tests.

7. Sample Size

One hundred subjects will be enrolled in this study.

8. Data Quality Assurance

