9.5. Analysis of Safety Endpoints

Treatment emergence will be evaluated for all AEs. Treatment-emergent adverse events (TEAEs) are those that occur on or after the same date and time of first dose of study drug. TEAEs will be coded using the most recent version of the Medical Dictionary of Regulatory Affairs (MedDRA) by assigning a preferred term and will be grouped by system, organ, and class (SOC) designation. AEs occurring after each vaccination up to the time of the next vaccination and separately over the whole study period will be summarized. Separate tables will be provided for solicited AEs reported within the 3 day period after each vaccination.

Each AE will be counted once only by preferred term for a given study subject within each post vaccination time period prior to the next vaccination or up to the 6-month follow-up visit after the last vaccination. If the same AE occurred on multiple occasions, the highest severity and relationship to investigational product will be assumed within each time period.

The summary tables will include an overall summary of number and percentage of subjects reporting each TEAE, summary by relationship, summary by severity will be presented by each vaccination period and overall.

Listings of each individual AE including start date, stop date, severity, relationship, duration, outcome, and actions taken will be provided.

Reactogenicity is defined as the total count of a set of solicited AEs that are expected after a vaccine. A regression analysis will be performed with reactogenicity as the dependent variable and anti-diphtheria titers as the independent variable to determine if there is an association. Anti-diphtheria titer is not expected to be normally distributed and will be natural log transformed. Null Hypothesis of no association between reactogenicity and anti-diphtheria titers will be tested on

Slope obtained using simple linear regression analysis at alpha=0.01 using two-sided tests. The null hypothesis states that the slope is equal to zero, and the alternative hypothesis states that the slope is not equal to zero. No adjustment for covariates will be made. The following SAS procedure PROC REG may be used.

```
Proc reg data=data;
Model reactogenicity =log(anti_diphtheria_titers);
Run;
```

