In addition, 2x2 tables will be created with presence or absence of moderate to severe reactogenicity versus high or not anti-diphtheria titers. Cut points of 75th percentile or 90th percentile of the anti-diphtheria titers will be used to define high level. The following SAS procedure PROC FREQ may be used.

```
Proc freq data=data;
Table reactogenicity*anti_diphtheria_titers/nopercent nocol;
Weight count;
Run;
```

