Preferred Term	xx (xx.x)	xx (xx.x)	xx (xx.x)	xx (xx.x)	xx (xx.x)	xx (xx.x)	xx (xx.x)	xx (xx.x)	xx (xx.x)

Note: Subjects are counted only once by preferred term at the highest severity grade and closest relationship to the investigational product.

R = Related to investigational product (possible, probable, definite). NR = Not related to investigational product (unrelated, unlikely).

Table 11: Contingency Table of Reactogenicity and Anti-diphtheria titers - ITT Population

Vaccination Number	Moderate to Severe Reactogenicity	Anti-diphtheria Titers		Total n (%)
		High = Yes n (%)	High = No n (%)	
1	Present	xx (xx.x)	xx (xx.x)	xx (xx.x)
	Absent	xx (xx.x)	xx (xx.x)	xx (xx.x)
	Total	xx (xx.x)	xx (xx.x)	xx (xx.x)
2	Present	xx (xx.x)	xx (xx.x)	xx (xx.x)
	Absent	xx (xx.x)	xx (xx.x)	xx (xx.x)
	Total	xx (xx.x)	xx (xx.x)	xx (xx.x)
3	Present	xx (xx.x)	xx (xx.x)	xx (xx.x)
	Absent	xx (xx.x)	xx (xx.x)	xx (xx.x)
	Total	xx (xx.x)	xx (xx.x)	xx (xx.x)
4	Present	xx (xx.x)	xx (xx.x)	xx (xx.x)
	Absent	xx (xx.x)	xx (xx.x)	xx (xx.x)
	Total	xx (xx.x)	xx (xx.x)	xx (xx.x)
5	Present	xx (xx.x)	xx (xx.x)	xx (xx.x)
	Absent	xx (xx.x)	xx (xx.x)	xx (xx.x)
	Total	xx (xx.x)	xx (xx.x)	xx (xx.x)
Overall	Present	xx (xx.x)	xx (xx.x)	
	Absent	xx (xx.x)	xx (xx.x)	
	Total	xx (xx.x)	xx (xx.x)	

Note: Reactogenicity is defined as the total count of a set of solicited AEs that are expected for up to 3 days after each vaccination. Cut points of 75th percentile of the anti-diphtheria titers is used to define high level.
 <Program Name: Time and Date>

Table 12: Summary of Serum Creatinine and Urinalysis Tests - ITT Population

Parameter (Unit)		Month 0	Month 3	Month 6	Month 9	Month 12
		n (%)				
Serum Creatinine	Low	xx (x.x)				
	High	xx (x.x)				
Specific Gravity	1.000	xx (x.x)				
	1.005	xx (x.x)				
	xx (x.x)				
pH	5	xx (x.x)				
	6	xx (x.x)				
	xx (x.x)				
Leucocytes	Negative	xx (x.x)				
	Trace	xx (x.x)				
	xx (x.x)				
Nitrite	Negative	xx (x.x)				
	Positive	xx (x.x)				
Protein (mg/dL)	Negative	xx (x.x)				
	Trace	xx (x.x)				
	xx (x.x)				
Glucose (mg/dL)	Normal	xx (x.x)				
	50	xx (x.x)				
	xx (x.x)				
Ketones	Negative	xx (x.x)				
	+/small	xx (x.x)				
	xx (x.x)				
Urobilinogen	Normal	xx (x.x)				
	1	xx (x.x)				
	xx (x.x)				
Bilirubin	Negative	xx (x.x)				
	+	xx (x.x)				
	xx (x.x)				
Blood/Hemoglobin (ery/uL)	Negative	xx (x.x)				
	Trace(blood)	xx (x.x)				
	xx (x.x)				

Table 13: Summary of Anti-tetanus Antibody Titers (IU/mL)

Visit	Statistics	ITT (N=xx)	Per-protocol (N=xx)

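### The illustrative 2x2 code in SAP 9.5 keeps the share of reactors with a high titer, not the reaction risk by titer group, and no effect estimate is planned for that table

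*SAP*

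**What the plan says.** SAP 9.5 plans two looks at anti-diphtheria titer and reactogenicity. The first is a regression: "A regression analysis will be performed with reactogenicity as the dependent variable and anti-diphtheria titers as the independent variable". Here reactogenicity is the total count of solicited AEs, and the test is on the "Slope obtained using simple linear regression analysis at alpha=0.01 using two-sided tests". The second is a cross-tabulation: "2x2 tables will be created with presence or absence of moderate to severe reactogenicity versus high or not anti-diphtheria titers". On the threshold, the text says "Cut points of 75th percentile or 90th percentile of the anti-diphtheria titers will be used to define high level". The note to the Table 11 shell in SAP Appendix A mentions one cut only: "Cut points of 75th percentile of the anti-diphtheria titers is used to define high level".

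For the cross-tabulation the SAP says "The following SAS procedure PROC FREQ may be used" and gives the statement "Table reactogenicity*anti_diphtheria_titers/nopercent nocol", followed by a `Weight` statement.

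The direction of interest is set out in SAP 5.3, and in the same terms in Protocol 11.2.7: "High anti-diphtheria titers will be assessed for an association with an increase in reactogenicity".

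The Table 11 shell has Present/Absent rows, High = Yes/No columns and n (%) cells, in a block for each vaccination and an overall block. It does not say what the percentages are out of. It has no line for a risk difference, ratio, interval or p-value. Protocol 12.2.3 describes the same 2x2 tables and names no effect measure either.

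**The concern.** In a PROC FREQ request of the form A*B, A forms the rows and B the columns. NOCOL removes the column percentages. NOPERCENT removes the percentages of the grand total. What remains is the counts and the row percentages, which here answer: of those who reacted, how many had a high titer? The plan treats titer as the predictor and reactogenicity as the outcome, so the useful percentage is: of those with a high titer, how many reacted? In this layout that is the column percentage, which the code suppresses.

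The share of subjects with a high titer is set by the percentile cut. A row percentage therefore partly reflects the analyst's choice of cut, and a reader could take it for a reaction rate. This matters because the 2x2 is the only planned analysis that relates titer to moderate-to-severe reactions. The regression slope covers only the total count of solicited AEs.

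**Working it through.** The documents give no expected rate, effect size or power for the 2x2, so there is no figure to reproduce. The check is a reading of the code plus worked tables.

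**Inputs from the documents.** N = 100 (SAP 7; Protocol 6.2). Cut at the 75th or 90th percentile (SAP 9.5).

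**Assumptions.** All reaction risks are assumed. All 100 subjects contribute, and the percentile is taken within the data being tabulated. The cut then gives 25 high and 75 not high, or 10 high and 90 not high.

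**Formulas.** Let *s* be the share with high titer, *p1* the reaction risk in the high group and *p0* the risk in the others.

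- Reaction risks (column percentages): *p1* and *p0*. Risk difference RD = *p1* − *p0*. Risk ratio RR = *p1*/*p0*.
- Share of reactors with high titer (row percentage): *s·p1* / [*s·p1* + (1 − *s*)·*p0*] = *s*·RR / [*s*·RR + 1 − *s*].

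The second expression contains only RR and *s*. The level of risk drops out and the cut point stays in.

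| Cut (high / not high) | Reactors, high and not high | Reaction risk, high v not high | RD (points) | RR | Kept by the code: high titer among reactors; among non-reactors |
|---|---|---|---|---|---|
| 75th (25 / 75) | 5 and 15 | 20.0% v 20.0% | 0.0 | 1.00 | 5/20 = 25.0%; 20/80 = 25.0% |
| 75th (25 / 75) | 5 and 8 | 20.0% v 10.7% | 9.3 | 1.88 | 5/13 = 38.5%; 20/87 = 23.0% |
| 75th (25 / 75) | 10 and 15 | 40.0% v 20.0% | 20.0 | 2.00 | 10/25 = 40.0%; 15/75 = 20.0% |
| 75th (25 / 75) | 10 and 8 | 40.0% v 10.7% | 29.3 | 3.75 | 10/18 = 55.6%; 15/82 = 18.3% |
| 90th (10 / 90) | 2 and 18 | 20.0% v 20.0% | 0.0 | 1.00 | 2/20 = 10.0%; 8/80 = 10.0% |
| 90th (10 / 90) | 4 and 18 | 40.0% v 20.0% | 20.0 | 2.00 | 4/22 = 18.2%; 6/78 = 7.7% |
| 90th (10 / 90) | 6 and 27 | 60.0% v 30.0% | 30.0 | 2.00 | 6/33 = 18.2%; 4/67 = 6.0% |

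What the table shows:

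- With no association, the kept percentage is simply the cut: 25% or 10%.
- With the same risks (40% v 20%), the share of reactors with high titer is 40.0% at one cut and 18.2% at the other. By the formula: 0.25 × 2 / (0.25 × 2 + 0.75) = 0.400, and 0.10 × 2 / (0.10 × 2 + 0.90) = 0.182.
- At the 90th percentile cut, risks of 40% v 20% and of 60% v 30% both give 18.2% of reactors.
- In the third row the row and column percentages are equal. That is a coincidence of those numbers.

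An interval would also tell the reader something that the percentages do not. For 40% v 20%, the risk difference of 20.0 points has a Wald 95% CI of −1.2 to 41.2 at the 75th percentile cut and −11.5 to 51.5 at the 90th.

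**The case against.** The other side has a good deal on its side.

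- **The code is optional.** The SAP says only that it may be used. The shell shows percentages in the margins as well, which NOPERCENT suppresses, so the shell is not straight output of this code. SAP 11 also requires code to be validated. A reader might infer that Table 11 will definitely report the reverse percentages. The documents do not establish that: the denominator is undefined, and the final table could still use columns. Equally, nothing else in the plan says which denominator is meant, and a review for consistency with the plan would not settle it.
- **The variables.** The names in the PROC FREQ code match those used for the count and the titer in the PROC REG code, so a reader might infer that raw values are being crossed. The documents do not support this. The sentence introducing the code specifies two yes/no variables, and the `Weight` statement fits a dataset already reduced to cell counts. The names read as placeholders.
- **Effect estimation.** A reader might infer that the SAP has no effect estimate for this association at all. It has one: the regression slope, in the right direction. The gap is confined to the 2x2. The slope does not fill it, because it models the total count and not moderate-to-severe reactions.
- **Consequences.** All four counts are printed, so risks, differences and ratios can be worked out by hand. The odds ratio is the same in either direction, and the row percentages point the same way as the risks. This is true, and it limits the weight of the point.
- **The remedy.** The 2x2 tables are supplementary and descriptive. A risk difference for each vaccination adds five intervals per cut with no multiplicity plan. That is fair, and it is a reason to label them descriptive and unadjusted.

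**Conclusion.** The point holds as a minor reporting and estimation matter. As illustrated, the code keeps a percentage that is conditional on reaction, moves with the percentile cut and is not a reaction risk. The plan's own question needs the risk within each titer group. Table 11 leaves the denominator open, and the 2x2 has no planned effect measure or interval.

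On the assumed rates, a true contrast of 20.0% v 10.7% (9.3 points) would appear as 38.5% v 23.0%. A fixed 40% v 20% contrast would show 40.0% or 18.2% of reactors with high titer, depending on the cut. These figures illustrate the mechanism; they do not predict this trial's data. They also assume that the cut is taken within the tabulated data. The SAP does not say whether it is set per vaccination or pooled, and with a pooled cut the high-titer share at a given vaccination could differ from 25% or 10%.

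No data are lost, and the regression test is unaffected.

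**What to change.** Before database lock:

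1. In the PROC FREQ code, replace NOCOL with NOROW (keeping NOPERCENT), or put titer in the rows and keep the present options.
2. In the Table 11 shell, state that percentages are subjects with moderate-to-severe reactogenicity out of all subjects in that titer group.
3. Add to the shell, for each vaccination, the risk difference (high minus not high) with an exact 95% CI, labelled descriptive and unadjusted.

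The cost is one changed code option, a further option for the risk difference, a footnote and a few extra shell lines. It also brings several unadjusted intervals: five per cut point, or ten if both cuts are tabulated. No new data are needed.

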9.6. Clinical Laboratory Data

Laboratory data for urinalysis results and serum creatinine levels will be presented as summary statistics by visit as well as in by-subject data listings. The number and percentage of subjects with serum creatinine > 1.5 x upper limit of normal and urine indicative for proteinuria (2+) or hematuria (blood \geq 50 erythrocytes/ μ L).

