11.2.6. Urinalysis and Serum Creatinine

A dipstick urinalysis will be performed that tests for protein, blood, leukocyte esterase, nitrates, pH, specific gravity, ketones, bilirubin, and glucose. A blood sample will also be collected for a serum creatinine test. These tests will be performed to monitor for the possible development of immune complex-mediated glomerular disease.

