12.2.3. Safety Analyses

AEs occurring after each vaccination up to the time of the next vaccination and separately over the whole study period will be summarized and presented in listings. Separate tables will be provided for solicited AEs reported within the 3 day period after each vaccination. AEs will be coded using the most recent version of the Medical Dictionary of Regulatory Activities (MedDRA) preferred terms and will be grouped by system, organ, and class (SOC) designation. The severity, frequency, and relationship of AEs to investigational product will be presented by preferred term by SOC grouping. Listings of each individual AE including start date, stop date, severity, relationship, outcome, and duration will be provided. Each AE (based on preferred terminology) will be counted once only for a given study subject within each post vaccination time period prior to the next vaccination or up to the 6-month follow-up visit after the last vaccination. If the same AE occurred on multiple occasions, the highest severity and relationship to investigational product will be assumed within each time period. Likewise an overall summary will be presented by counting each AE one time over the entire study period.

Reactogenicity is defined as the total count of a set of solicited AEs that are expected after a vaccine. A regression analysis will be performed with reactogenicity as the dependent variable and anti-diphtheria titers as the independent variable to determine if there is an association. In addition, 2x2 tables will be created with presence or absence of moderate to severe reactogenicity versus high or not anti-diphtheria titers. Cut points of 75th percentile or 90th percentile of the anti-diphtheria titers will be used to define high level.

Urinalysis results and serum creatinine levels will be presented as summary statistics over time.

The final disposition of all subjects (completed the study or withdrawn early and reason for early withdrawal) will be summarized and provided in a listing. Medications will be presented in a listing.

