Subject Number	Date of Tdap Vaccination	Visit	Tdap NDC Number	Tdap Lot Number	Problems with the injection?	Specify
xxxx	dd/mmm/yyyy	Month 0			Y/N	Verbatim text

Programming Note: Sorted by subject number, exam date.

<Program Name: Time and Date>

Listing 9: Serum Creatinine and Urinalysis Tests Results – ITT Population

Subject Number	Date of Collection	Visit	Test Name (Unit)	Result	Reason not Collected
xxxx	dd/mmm/yyyy	Screening (all Visits)	Creatinine (Unit) Glucose	Xxx Xxx	Xxx Xxx/xx

Programming Note: Sorted by subject number, Exam Date .

<Program Name: Time and Date>

Listing 10: Anti-tetanus and Anti-diphtheria Antibody Tests Results – ITT Population

Subject Number	Date of Collection	Visit	Plasma Sample Identification #	Test Name (Unit)	Result	Reason not Collected, Specify
xxxx	dd/mmm/yyyy	Screening (all Visits) Unscheduled		xxx xxx/xx	Xxx Xxx/xx	Xxx Xxx/xx

Programming Note: Sorted by subject number, Exam Date.

<Program Name: Time and Date>

Listing 11: Adverse Events – ITT Population

Subject Number	AE Name/ MedDRA PT ^a / SOC ^b	Onset Date/ Stop Date	Onset Day/ Duration (Days)	Severity	TEAE/ Vaccine Number	Serious? /SAE Description	Outcome	Relationship to Study Product/ Action Taken	Other Actions, Specify
xxxx	xxxx/	dd/mmm/yyyy	Xx/xx	Mild		Y/Xxx	Resolved	Unrelated	
	xxxx /	dd/mmm/yyyy		Moderate		N	Resolved	Unlikely	
	xxxx	or Ongoing		Severe			with sequelae	Possible Probable	

^aPT=Preferred Term; ^bSOC=System, Organ, and Class

Programming Note: Sorted by Subject Number, Onset Date.

<Program Name: Time and Date>

Listing 12: Solicited Adverse Events – ITT Population

Subject Number	Vaccination Number	AE Name/ MedDRA PT ^a / SOC ^b	Onset Date/ Stop Date	Onset Day/ Duration (Days)	Severity	TEAE/ Vaccine Number	Serious?	Outcome	Relationship to Study Product/ Action Taken
xxxx	1	xxxx/	dd/mmm/yyyy	Xx/xx	Mild		Y	Resolved	Unrelated
	2	xxxx /	dd/mmm/yyyy		Moderate		N	Resolved with sequelae	Unlikely Possible Probable
		xxxx	or Ongoing		Severe				

^aPT=Preferred Term; ^bSOC=System, Organ, and Class

Note: Solicited AEs reported within the 3 day period after each vaccination is listed.

Programming Note: Sorted by Subject Number, Onset Date.

<Program Name: Time and Date>

Listing 13: Adverse Events Leading to Withdrawal – ITT Population

Subject Number	AE Name/ MedDRA PT ^a / SOC ^b	Onset Date/ Stop Date	Onset Day/ Duration (Days)	Severity	TEAE/ Vaccine Number	Serious?	Outcome	Relationship to Study Product/ Action Taken	Other Actions, Specify

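### The renal criterion in SAP 9.6 is an incomplete sentence that, read literally, needs a creatinine and a urine finding together; Table 12 has no row for it and no numeric, within-subject or repeat-finding summary

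*SAP*

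**What the plan says.** Protocol 11.2.6 gives the purpose of the dipstick urinalysis and serum creatinine: "These tests will be performed to monitor for the possible development of immune complex-mediated glomerular disease". Under Protocol 8.8 and Table 4 (footnote c), both are measured 1 to 3 days after each of the five vaccinations, or at the next visit if the subject does not return in that time.

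For analysis, Protocol 12.2.3 states: "Urinalysis results and serum creatinine levels will be presented as summary statistics over time". SAP 9.6 says that the data "will be presented as summary statistics by visit as well as in by-subject data listings" and then adds the criterion: "The number and percentage of subjects with serum creatinine > 1.5 x upper limit of normal and urine indicative for proteinuria (2+) or hematuria", with blood set at 50 erythrocytes/µL or more. SAP 9.1 defines the summary for continuous variables as n, mean, SD, median, minimum and maximum.

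The shell in SAP Appendix A, "Table 12: Summary of Serum Creatinine and Urinalysis Tests - ITT Population", has columns for Months 0, 3, 6, 9 and 12. Creatinine has two rows, Low and High, as n (%). Urine protein and blood are given by dipstick category. The by-subject values go to "Listing 9: Serum Creatinine and Urinalysis Tests Results" in Appendix B.

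**The concern.** Safety of five repeated doses is the primary objective, and these tests are the only laboratory check aimed at a named renal harm. Three things stand between the data and a usable answer.

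- The criterion can be programmed in more than one way, and the literal way is the least sensitive.
- The table meant to report it has no place for it, or for the numeric creatinine summary.
- Each subject has up to five serial results, yet every planned count is taken visit by visit, so the table cannot say whether a finding belongs to one subject repeatedly or to several subjects once.

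A report built from that table could state that no renal signal was seen when the data contain one.

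**Working it through.** The plan states no detection rate or fold-rise for this criterion, so there is no figure to reproduce. The check compares the text with the shell and then sizes the creatinine flag.

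**1. What the sentence counts.** *Joint* is the literal reading: creatinine above 1.5 x ULN together with either urine finding. *Separate* is three independent flags, with protein read as 2+ or more.

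| Subject's result | Joint | Separate |
|---|---|---|
| Creatinine >1.5 x ULN, urine clear | not counted | counted |
| Protein 2+, creatinine normal | not counted | counted |
| Protein 3+, creatinine normal | not counted | counted |
| Blood ≥50 ery/µL, creatinine normal | not counted | counted |
| Creatinine >1.5 x ULN and protein 3+, blood below 50 | not counted if 2+ is exact | counted |

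The blood limit carries a greater-or-equal sign and the protein limit does not, so the last row is a real programming choice.

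**2. Text against shell.**

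| Promised in SAP 9.1 and 9.6 | In Table 12 |
|---|---|
| n, mean, SD, median, min, max for creatinine by visit | absent; Low and High counts only |
| n (%) meeting the renal criterion | no row |

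Neither the text nor the shell plans a within-subject change or a repeat-finding count.

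**3. What visit counts can show.** Suppose one subject is blood-positive at each of Months 6, 9 and 12. The row reads 1, 1, 1. That fits any number of distinct subjects from 1 to 3. If one subject is protein-positive and one is blood-positive in the same column, the number positive for both is 0 or 1. The table cannot tell which.

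**4. Size of the creatinine flag.** The documents give no ULN and no donor values. Assumptions: own value *b* between 0.5 and 1.0 of ULN, and High meaning above ULN.

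Rise needed for the flag = 1.5 / *b*. Rise needed for High = 1 / *b*. Level after a 50% rise = 1.5 × *b*.

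| *b* (x ULN) | Flag needs more than | High needs more than | After +50% (x ULN) | Flag | High |
|---|---|---|---|---|---|
| 0.5 | 3.0-fold | 2.0-fold | 0.75 | no | no |
| 0.6 | 2.5-fold | 1.67-fold | 0.90 | no | no |
| 0.75 | 2.0-fold | 1.33-fold | 1.125 | no | yes |
| 0.9 | 1.67-fold | 1.11-fold | 1.35 | no | yes |
| 1.0 | 1.5-fold | 1.0-fold | 1.50 | no | yes |

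A 50% rise escapes both rows when *b* is at or below 1/1.5 = 0.67 ULN.

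**5. Illustration over a population (assumed).** Take own values as normal with mean 0.75 ULN and 97.5th percentile at ULN, so SD = (1 − 0.75)/1.96 = 0.128.

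- All rise by 50%: the flag catches P(*b* > 1.0) = 2.5%. High catches P(*b* > 0.667) = 74%. About 26% appear in neither.
- All double: the flag catches P(*b* > 0.75) = 50%. High catches P(*b* > 0.5) = 97.5%.

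**6. What the schedule allows.** The first renal sample falls after dose 1. None is scheduled before vaccination, and Table 4 has no renal row at Months 13 or 18. A ratio to the earliest sample can be computed, but it is not change from a pre-vaccination baseline.

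**The case against.** A reader might infer that the criterion demands roughly a doubling of creatinine in a typical donor. The documents do not support that as a statement of fact: they contain no reference range and no donor values. The figure is 2.0-fold at 0.75 ULN and anything from 3.0- to 1.5-fold across the assumed range.

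A reader might also infer that early glomerular disease would go unseen. That is too strong, for three reasons.

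- Table 12 reports urine protein and blood by category at every vaccination month, and the protein categories continue past trace. A urine finding with normal creatinine, including one above 2+, would therefore appear there as a visit count.
- Listing 9 gives every result by subject and date. With 100 subjects, a reviewer could trace change and repetition by hand.
- Abnormal laboratory findings fall within the adverse event definition (Protocol 11.2.8.1.1, SAP 5.1), and the medical monitor follows trends in reported events (Protocol 10).

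These safeguards stand, but they are partial. A listing of raw values supplies no count or rule. No renal threshold is given for calling a result an adverse event, and a rise within the normal range need not be called abnormal. The medical monitor's trend review in Protocol 10 covers reported events.

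It is also fair to say that the numeric creatinine summary is already promised in the text, so its absence from Table 12 is a shell error, and that any cut on a within-subject ratio is for the sponsor to choose. Both are accepted.

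**Conclusion.** The point holds as a defect in the criterion's wording and in its tabulation, and it should be corrected before database lock. Three parts rest on the documents alone: the literal *and* with a bare 2+, the missing Table 12 rows, and the lack of any within-subject, co-occurrence or repeat-finding summary.

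The fold-rises rest on assumed own values of 0.5 to 1.0 ULN. The 2.5% and 74% figures rest further on an assumed distribution, and they also show that the High row recovers much of what the flag misses. What follows is that a renal signal may be missed in the summary tables. It does not follow that the study as a whole could not see one.

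**What to change.** Amend SAP 9.6 and Table 12, using data already collected:

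1. **Creatinine.** Report n, mean, SD, median, minimum and maximum by visit. Add the ratio of each later value to the subject's earliest sample, labelled as taken after dose 1 and not a pre-vaccination baseline. Give n (%) above a reporting cut chosen by the sponsor (for example, 1.5 times the subject's own earliest value).
2. **Flags.** Complete the sentence and report three separate flags: creatinine above 1.5 x ULN; protein 2+ or more; blood 50 ery/µL or more. Show each by visit and once per subject overall.
3. **Patterns.** Report n (%) of subjects with protein and blood flagged in the same sample, and n (%) with the same flag at two consecutive vaccination tests. Add a note that a first flag at Month 12 cannot be checked for persistence, because no renal test is scheduled at Months 13 or 18.

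The cost is SAP wording and a few table rows; no sample or visit is added. There are two downsides. A within-subject ratio will flag some laboratory noise, which the consecutive-test row helps to sort out, although those tests are about three months apart. The post-dose-1 reference may also understate a change already present after dose 1. These are reporting summaries and set no rule for managing subjects.
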